6.3. Lifestyle Restrictions

Not applicable.

6.4. Screen Failures

Patients who are entered into the study but do not meet the enrollment criteria for participation in this study (screen failure) may be rescreened a maximum of 2 times. The interval between screen failure and rescreenings should be at least 4 weeks. At the time of rescreening, the individual must sign a new ICF, repeat all necessary screening procedures, and will be assigned a new identification number.

If a patient undergoes rescreening, radiographic images acquired as part of initial screening and within 6 months of randomization may be used.

7. Treatments

7.1. Treatments Administered

This study involves a comparison of placebo, baricitinib 1-mg, baricitinib 2-mg, and baricitinib 4-mg administered orally once a day. [Table JAIN.3](#) shows the treatment regimens.

Table JAIN.3. Treatment Regimens

Regimen	Investigational Product Supplied	Dose
Baricitinib 4-mg QD ^a	Baricitinib 4-mg tablets	3 tablets per day
	Placebo to match 2-mg tablets	
	Placebo to match 1-mg tablets	
Baricitinib 2-mg QD	Baricitinib 2-mg tablets	3 tablets per day
	Placebo to match 4-mg tablets	
	Placebo to match 1-mg tablets	
Baricitinib 1-mg QD	Baricitinib 1-mg tablets	3 tablets per day
	Placebo to match 4-mg tablets	
	Placebo to match 2-mg tablets	
Placebo QD	Placebo to match 4-mg tablets	3 tablets per day
	Placebo to match 2-mg tablets	
	Placebo to match 1-mg tablets	

Abbreviation: QD = once daily.

^a The baricitinib dose for patients randomized to the 4-mg QD treatment group who have renal impairment (defined as eGFR <60 mL/min/1.73 m²) will be 2-mg QD.

The investigator or his/her designee is responsible for the following:

- explaining the correct use of the investigational agent(s) to the patient
- verifying that instructions are followed properly
- maintaining accurate records of investigational product dispensing and collection
- at the end of the study returning all unused medication to Lilly, or its designee, unless the sponsor and sites have agreed all unused medication is to be destroyed by the site, as allowed by local law.

7.1.1. Packaging and Labeling

The sponsor (or its designee) will provide the following investigational products:

- tablets containing 4-mg of baricitinib
- tablets containing 2-mg of baricitinib
- tablets containing 1-mg of baricitinib
- placebo tablets to match baricitinib 4-mg tablets, 2-mg tablets, and 1-mg tablets.

Packaging for each dose will include 3 tablets per day. Each tablet has a distinctive shape and color, 4-mg versus 2-mg versus 1-mg, and each strength tablet has a matching placebo. Each

active dose package will contain the appropriate active strength tablet, and corresponding placebo tablets for the other strengths, as noted in [Table JAIN.3](#).

Investigational product tablets will be provided in blister packs.

Clinical trial materials will be labeled according to the country's regulatory requirements.

7.2. Method of Treatment Assignment

Patients who meet all criteria for enrollment will be randomized in a 1:1:2:1 ratio to receive placebo QD, baricitinib 1-mg QD, 2-mg QD, or 4-mg QD to double-blind treatment at Visit 2 (Week 0). Randomization will be stratified by geographic region if the planned country allocation justifies, and disease severity at baseline (IGA 3 versus 4). Assignment to treatment groups will be determined by a computer-generated random sequence using an IWRS. The IWRS will be used to assign cartons, each containing 4 blister packs of double-blind investigational product tablets to each patient, starting at Visit 2 (Week 0), and at each visit up to and including Visit 28 (Week 200). Site personnel will confirm that they have located the correct carton by entering a confirmation number found on the carton into the IWRS.

7.2.1. Selection and Timing of Doses

The investigational product (3 tablets from blister pack) should be taken once daily without regard to food and, if possible, at approximately the same time every day, usually at the start of the patient's day, to aid patient compliance.

7.2.2. Dose Adjustment for Renal Impairment

The rationale of dose adjustment for patients with documented renal impairment (defined as screening eGFR ≥ 40 to < 60 mL/min/1.73 m²) is detailed in Section [5.5.1](#).

The dose adjustment for renal impairment will be managed by IWRS to ensure maintenance of the treatment blind. The eGFR value from the screening visit (Visit 1) will be entered into IWRS at Visit 2, and IWRS will assign the treatment doses accordingly.

Patients with documented renal impairment (defined as screening eGFR ≥ 40 to < 60 mL/min/1.73 m²), who are randomized to the 4-mg active treatment arm will receive a dose of 2-mg QD by the IWRS. For patients randomized to the 2-mg dose or 1-mg dose, there will be no dose adjustment based on renal function.

No dose adjustment will be made for patients with screening eGFR ≥ 60 mL/min/1.73 m². These patients who are randomized to active treatment will receive their assigned dose, either baricitinib 4-mg, 2-mg, or 1-mg, respectively.

During the study, for patients with documented renal impairment when the subsequent eGFR falls < 30 mL/min/1.73 m², investigational product will be withheld until their eGFR becomes ≥ 40 mL/min/1.73 m², whereupon the investigational product dosing may resume. For patients with screening eGFR ≥ 60 mL/min/1.73 m², when the subsequent eGFR falls to < 40 mL/min/1.73 m², investigational product will be withheld until their eGFR becomes ≥ 50 mL/min/1.73 m², whereupon the investigational product dosing may resume (Section [8.1.1](#)).

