5.1. Overall Design

Study I4V-MC-JAIN (JAIN) is a Phase 3, multicenter, double-blind, randomized, placebo-controlled study evaluating the safety and efficacy of baricitinib 1-mg QD, 2-mg QD, and 4-mg QD in combination with TCS in patients with moderate-to-severe atopic dermatitis (AD) who have experienced failure of cyclosporine, or are intolerant to, or have a contraindication to, cyclosporine. The study is divided into 5 periods: a 5-week Screening period, a 1-year Double-Blind Treatment period (Week 0 through Week 52), a 1-year double-blind, long-term extension (Week 52 through Week 104) that includes a randomized downtitration substudy, a bridging extension that may last up to 96 weeks (Week 104 to up to Week 200) and a 4-week Post-Treatment Follow-Up period.

Approximately 500 patients ≥ 18 years of age will be randomized at a 1:1:2:1 ratio to receive placebo QD, baricitinib 1-mg QD, baricitinib 2-mg QD, or baricitinib 4-mg QD (100 patients in the placebo group; 100 patients each in the baricitinib 1-mg and 4-mg groups; and 200 patients in the baricitinib 2-mg treatment group). Patients will be stratified at randomization according to disease severity (Investigator's Global Assessment [IGA] 3 versus 4) and geographic region if the planned country allocation justifies.

All procedures to be conducted during the study, including timing of all procedures, are indicated in the Schedule of Activities (Section 2). Section 9.4.4 describes collection of laboratory samples; [Appendix 2](#), [Appendix 4](#), and [Appendix 5](#) list the specific laboratory tests that will be performed for this study. Study governance considerations are described in detail in [Appendix 3](#). Section 10.3.7.1 outlines information regarding the data monitoring committee (DMC) and interim analyses.

[Figure JAIN.1](#) illustrates the study design.

Abbreviations: AD = atopic dermatitis; eGFR = estimated glomerular filtration rate; ET = early termination; IGA = Investigator’s Global Assessment; IP = investigational product; PPD = purified protein derivative; QD = once daily; TB = tuberculosis; TCS = topical corticosteroids; V = visit; W = week.

^a Applicable to patients taking topical treatments (excluding emollients) or systemic treatments for AD at the time of screening.

^b Maximum dose of baricitinib for patients with renal impairment (defined as eGFR <60 mL/min/1.73 m²) will be 2-mg QD.

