5.1.3.2. Patients Not Eligible for the Substudy

Beginning at Week 52,

- Patients with an IGA ≥ 3 who
 - are in the baricitinib 2-mg, 1-mg, and placebo treatment groups will be automatically rerandomized at a 1:1 ratio to baricitinib 2-mg QD or baricitinib 4-mg QD.

- are in the baricitinib 4-mg treatment group will remain on 4-mg QD (see “Rescue during Period 3” Section 7.7.5.2).
- Patients with an IGA 0, 1, or 2 who
 - are in the baricitinib 4-mg or 2-mg treatment groups and who are not eligible for the substudy (i.e., have study drug interrupted at Week 52, or have received high- or ultra-high potency TCS in the previous 14 days), or are in the placebo or baricitinib 1-mg groups will continue in their current treatment group.
 - Patients who experience a worsening of symptoms of AD such that IGA increases to ≥ 3 will be rerandomized at a 1:1 ratio to baricitinib 2-mg QD or baricitinib 4-mg QD. Patients in the baricitinib 4-mg group will remain on 4-mg.

This option for rescue is only available once for each patient and will be assigned by IWRS; investigators will remain blinded to treatment assignments. The investigator may reinstate background TCS therapy (e.g., triamcinolone 0.1% cream and/or hydrocortisone 2.5% ointment), provided the patients are not currently using TCS, and may prescribe high- or ultra-high-potency TCS following the guidelines for use of rescue therapies (see Section 7.7.5).

Once a patient has an IGA ≥ 3 in Period 3, the investigator will know that a patient is on the highest dose of baricitinib that he/she will receive in the study; therefore, if AD symptoms remain unacceptable then discontinuation should be considered.

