5.5.1. Rationale for Dose Adjustment for Renal Impairment

Baricitinib exposure increases with decreased renal function. Based on PK simulations of baricitinib exposures for the mild and moderate categories of renal function (stratified as estimated glomerular filtration rate [eGFR] 60 to <90 mL/min/1.73 m² and eGFR 30 to <60 mL/min/1.73 m², respectively), dose adjustment is not required for patients with eGFR ≥ 60 mL/min/1.73 m². Patients with eGFR <60 mL/min/1.73 m² who are randomized to the 4-mg dose will receive a dose of 2-mg QD, which will ensure that exposures do not exceed those of the 4-mg QD dose in patients with eGFR ≥ 60 mL/min/1.73 m². For patients randomized to the 2-mg dose or 1-mg dose, there will be no dose adjustment based on renal function. The dose adjustment for renal impairment will be managed by IWRS to ensure maintenance of the treatment blind. This study will not enroll patients with screening eGFR <40 mL/min/1.73 m². See Section 8.1.1 for eGFR thresholds that trigger interruption of investigational product.

The procedure for dose adjustment based on renal function (eGFR) during the study is detailed in Section 7.2.2.

6. Study Population

Prospective approval of protocol deviations to recruitment and enrollment criteria, also known as protocol waivers or exemptions, are not permitted.

Study investigator(s) will review patient history and screening test results at Visit 1 and Visit 2 to determine if the patient meets all inclusion and none of the exclusion criteria to qualify for randomization in the study. All screening activities must be completed and reviewed before the patient is randomized.

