8.1. Discontinuation from Study Treatment

8.1.1. Temporary Interruption of Investigational Product

In some circumstances, it may be necessary to temporarily interrupt treatment as a result of AEs or abnormal laboratory values that may have an unclear relationship to investigational product. For example, investigational product should be temporarily interrupted if the patient experiences a cardiovascular AE considered to be related to study treatment, is graded as moderate (Grade 2 according to Common Terminology Criteria for Adverse Events [CTCAE] Version 3.0), and that does not resolve promptly with supportive care. Except in cases of emergency, it is recommended that the investigator consult with Lilly (or its designee) before temporarily interrupting therapy for reasons other than those defined in [Table JAIN.4](#).

For the abnormal laboratory findings and clinical events (regardless of relatedness) listed in [Table JAIN.4](#), specific guidance is provided for temporarily interrupting treatment and when treatment may be restarted. Retest frequency and timing of follow-up laboratory tests to monitor the abnormal finding are at the discretion of the investigator. Investigational product that was temporarily interrupted because of an AE or abnormal laboratory value not specifically covered in [Table JAIN.4](#) may be restarted at the discretion of the investigator.

Table JAIN.4. Medical and Laboratory Criteria for Temporary Interruption of Investigational Product

Hold Investigational Product if the Following Laboratory Test Results or Clinical Events Occur	Investigational Product May Be Resumed When
WBC count <2000 cells/ μ L (<2.00x10 ³ / μ L or <2.00 GI/L)	WBC count \geq 2500 cells/ μ L (\geq 2.50x10 ³ / μ L or \geq 2.50 GI/L)
ANC <1000 cells/ μ L (<1.00x10 ³ / μ L or <1.00 GI/L)	ANC \geq 1200 cells/ μ L (\geq 1.20x10 ³ / μ L or \geq 1.20 GI/L)
Lymphocyte count <500 cells/ μ L (<0.50x10 ³ / μ L or <0.50 GI/L)	Lymphocyte count \geq 750 cells/ μ L (\geq 0.75x10 ³ / μ L or \geq 0.75 GI/L)
Platelet count <75,000/ μ L (<75x10 ³ / μ L or <75 GI/L)	Platelet count \geq 100,000/ μ L (\geq 100x10 ³ / μ L or \geq 100 GI/L)
eGFR <40 mL/min/1.73 m ² (from serum creatinine) for patients with screening eGFR \geq 60 mL/min/1.73 m ²	eGFR \geq 50 mL/min/1.73 m ²
eGFR <30 mL/min/1.73 m ² (from serum creatinine) for patients with screening eGFR \geq 40 to <60 mL/min/1.73 m ²	eGFR \geq 40 mL/min/1.73 m ²

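### Rerandomisation to baricitinib 4-mg at or after Week 52 has no eGFR check, so a patient screened at 60 or above and now at 40 to 59 can newly start 4-mg

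*Protocol*

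**What the plan says.** All eGFR values are in mL/min/1.73 m².

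**Rationale.** Protocol Section 5.5.1 states that exposure rises as renal function falls. Patients below 60 who are randomised to 4-mg receive 2-mg, "which will ensure that exposures do not exceed those of the 4-mg QD dose in patients with eGFR" of 60 or more. It then refers onward: "The procedure for dose adjustment based on renal function (eGFR) during the study is detailed in Section 7.2.2".

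**Procedure.** Section 7.2.2 defines documented renal impairment as a screening eGFR of 40 to below 60. Dose is set once: "The eGFR value from the screening visit (Visit 1) will be entered into IWRS at Visit 2, and IWRS will assign the treatment doses accordingly". For patients screened at 60 or above there is no adjustment: "These patients who are randomized to active treatment will receive their assigned dose". Later eGFR values act only through holds. If screening was 60 or above, drug is withheld below 40 and may resume at 50. If screening was 40 to below 60, it is withheld below 30 and may resume at 40. Table JAIN.4 repeats these tiers.

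**Short statements that name no visit.** Figure JAIN.1 footnote b, repeated under the SAP's design figure, says "Maximum dose of baricitinib for patients with renal impairment" is 2-mg. Table JAIN.3 footnote a sets 2-mg as "The baricitinib dose for patients randomized to the 4-mg QD treatment group who have renal impairment".

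**Rerandomisation.** Under Section 5.1.3.2, patients with IGA 3 or more on placebo, 1-mg or 2-mg who are not in the substudy "will be automatically rerandomized at a 1:1 ratio to baricitinib 2-mg QD or baricitinib 4-mg QD". Sections 5.1.4 and 7.7.5.2 carry this through Period 4. None of the three mentions eGFR or a new renal entry in IWRS.

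**The concern.** Rerandomisation is a new dose assignment made a year or more after the only renal value the dosing rule uses. Half of those rerandomised step up to 4-mg, and they stay on the assigned dose for the rest of the study, up to Week 200.

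The argument in Section 5.5.1 concerns renal function while the drug is being taken. For a patient who has moved from 60 or above at screening to 40 to 59, a new 4-mg start is twice the dose that the rationale relies on below 60. The assurance that exposure stays within that of 4-mg at 60 or above no longer covers that patient. Sites are blinded to dose, so an investigator who sees the laboratory report cannot apply a cap. Only IWRS can.

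**Working it through.** The plan gives no figure to reproduce. The check is of the rule, then of timing and size.

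**1. The rule.** Inputs are Section 7.2.2 and Table JAIN.4. I applied them to a patient rerandomised to 4-mg, taking the stored screening value to govern that assignment and drug not already on hold. The last column applies a cap to the most recent value instead.

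| Screening eGFR | Current eGFR | 7.2.2 as written | Cap on most recent value |
|---|---|---|---|
| 75 | 35 | hold | hold |
| 75 | 45 | 4-mg | 2-mg |
| 75 | 55 | 4-mg | 2-mg |
| 75 | 65 | 4-mg | 4-mg |
| 50 | 35, 45 or 55 | 2-mg | 2-mg |
| 50 | 65 | 2-mg | 4-mg |

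The patients for whom the written rule gives the higher dose are those screened at 60 or above and now at 40 to 59.

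**2. Age of the renal value.** Screening is 8 to 35 days before Week 0, and Week 52 is day 364. The screening eGFR is then 364 + 8 = 372 to 364 + 35 = 399 days old.

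In the Schedule of Activities, chemistry (which includes eGFR) is drawn at Weeks 0, 4, 8, 12, 16, 24, 32, 40, 52, 64, 76, 92 and 104, then every 16 weeks to Week 200. Of the 14 scheduled visits from Week 52 to Week 184, 10 have chemistry. A same-day central result may not be back when dose is assigned, so I counted days from the previous scheduled draw, ignoring visit windows:

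- Week 52: (52 − 40) × 7 = 84 days.
- Shortest, for example Week 56: (56 − 52) × 7 = 28 days.
- Longest, for example Week 92: (92 − 76) × 7 = 112 days.

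**3. Size.** Section 5.1 plans 100 placebo, 100 1-mg and 200 2-mg patients, 400 in all. If every one were rerandomised, 400 × 1/2 = 200 would be assigned 4-mg. The true number is lower because of dropout, and because 2-mg patients who enter the substudy can return only to 2-mg.

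The following are assumptions, not in the documents: 40–80% of the 200 placebo and 1-mg patients and 20–60% of the 200 2-mg patients are rerandomised, and 1–5% of new 4-mg starts have moved from 60 or above to 40 to 59.

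- Low: 0.5 × (200 × 0.40 + 200 × 0.20) = 60 new starts; 60 × 0.01 = 0.6 patients.
- High: 0.5 × (200 × 0.80 + 200 × 0.60) = 140 new starts; 140 × 0.05 = 7 patients.

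Wider assumptions (30–100% of the 400 rerandomised, 0.5–5% declined) give 400 × 0.30 × 0.5 × 0.005 = 0.3 to 400 × 1 × 0.5 × 0.05 = 10 patients.

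**The case against.** A reader might infer that the protocol breaks its own cap. The text does not go that far. Section 7.2.2 defines documented impairment by screening eGFR, and Section 5.5.1 names it as the procedure, so the short footnotes can be read as using that definition. Table JAIN.3 footnote a and Section 5.5.1 speak only of patients randomised to 4-mg. Only Figure JAIN.1 footnote b reads as a general maximum. The on-study procedure promised in Section 5.5.1 does exist, as the hold and resume tiers. All of this stands.

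A reader might also infer that 4-mg at 40 to 59 is ruled out during the study. It is not. When screening was 60 or above, the protocol accepts continuing 4-mg at 40 to 59 and resuming it at 50 or above. It follows that a recheck only at rerandomisation leaves some patients at the same eGFR on different doses, and that a patient rerandomised at 61 who later falls to 45 stays on 4-mg. That is a fair limit on what the change achieves. It does not settle whether a new step up should rest on a year-old value. Tolerating an established dose under monitoring is a different decision from starting a higher one.

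Nor is the first randomisation fully protected: a patient at 65 at Visit 1 and 45 on the Week 0 sample also receives 4-mg. There, however, the value is 8 to 35 days old.

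There are backstops too, namely the hold below 40 and investigator review of laboratory reports. Neither lowers a dose at 40 to 59.

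**Conclusion.** The gap is real and worth closing. As written, the renal rule uses only the Visit 1 eGFR and rerandomisation has no renal condition, so a placebo, 1-mg or 2-mg patient screened at 60 or above and now at 40 to 59 can newly start 4-mg without the exposure assurance of Section 5.5.1. It should not be described as a contradiction, or as evidence that 4-mg at 40 to 59 is prohibited.

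The number affected is unknown and likely small. The ranges of 0.6 to 7 and 0.3 to 10 patients rest wholly on assumed rerandomisation and decline rates. The IWRS specification is not among the documents, so an unreported check cannot be excluded; if one exists, Section 7.2.2 should say so. No sample size, power or alpha figure changes: the SAP makes Period 3 and 4 analyses descriptive and without multiplicity adjustment.

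**What to change.** In Sections 7.2.2 and 5.1.3.2, require the most recent available central-laboratory eGFR to be entered in IWRS for every patient at Week 52 and at any later visit with IGA 3 or more, whatever the arm or substudy status, so that the prompt does not reveal treatment. Have IWRS dispense 2-mg under blind to any patient newly rerandomised to 4-mg whose value is below 60. Leave patients already assigned 4-mg, and substudy retreatment, under the existing hold and resume tiers. In Figure JAIN.1 footnote b and Table JAIN.3 footnote a, say which eGFR applies: screening at Week 0, most recent at rerandomisation. Also state what happens to a patient screened at 40 to below 60 whose latest value is 60 or more. Keeping 2-mg, as Section 7.2.2 now implies, is the cautious choice, because that patient's hold threshold is 30.

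The cost is one extra IWRS entry at these visits and a few sentences of text. No new samples are needed, and Appendix 2 already allows a repeat panel if a value looks old or borderline. The value may be up to 112 days old. A few patients counted in the 4-mg group will receive 2-mg, including some 2-mg nonresponders whose dose does not change. Analyse them by assigned arm as planned, and list them.

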7.3. Blinding

This is a double-blind study. To preserve the blinding of the study, a minimum number of Lilly personnel will see the randomization table and treatment assignments before the study is complete. All study assessments will be performed by study personnel who are blinded to the patient's treatment group. Except in clinical circumstances where unblinding is required, the patients, investigators, Lilly study team, and any personnel interacting directly with patients or investigative sites will remain blinded to baricitinib and placebo assignment until after completion of the double-blinded treatment periods. It is expected that the need for unblinding a patient's treatment prior to completion of the double-blinded treatment periods will be extremely rare. Every effort should be made to preserve the blind unless there is a compelling reason that knowledge of the specific treatment would alter the medical care of the patient. In case of an emergency, the investigator has the sole responsibility for determining if unblinding of a patient's treatment assignment is warranted for medical management of the event. Patient safety must always be the first consideration in making such a determination. If a patient's treatment assignment is unblinded, Lilly must be notified immediately. If the investigator decides that unblinding is warranted, it is the responsibility of the investigator to promptly document the decision and rationale and notify Lilly as soon as possible.

Emergency unblinding for AEs may be performed through the IWRS. This option may be used ONLY if the patient's well-being requires knowledge of the patient's treatment assignment. All unblinding events are recorded and reported by the IWRS. If an investigator, site personnel performing assessments, or patient is unblinded, the patient must be discontinued from the study. In cases where there are ethical reasons to have the patient remain in the study, the investigator must obtain specific approval from a Lilly clinical research physician for the patient to continue in the study.

Processes to maintain blinding during the interim analysis conducted by the DMC are described in Section [10.3.7.1](#).

